8.3.4. Ophthalmic Examinations

Full ophthalmic examination will be performed by an ophthalmologist if treatment emergent ocular AEs are observed ([SoA](#)) including best corrected visual acuity, slit lamp examination, and intraocular pressure.

For participants with clinical suspicion of retinal abnormalities occurring during study conduct (ie, photopsia, metamorphopsia, impairment of visual acuity) or RVO, additional assessments of OCT, dilated fundoscopy, optical coherence tomography (for RPED), and fluorescein angiography of the central 30 degrees (for RVO) should be conducted if deemed clinically necessary.

8.3.5. Clinical Safety Laboratory Assessments

See [Appendix 2](#) for the list of clinical safety laboratory tests to be performed and the [SoA](#) for the timing and frequency. All protocol-required laboratory assessments, as defined in [Appendix 2](#), must be conducted in accordance with the laboratory manual and the [SoA](#). Unscheduled clinical laboratory measurements may be obtained at any time during the study to assess any perceived safety issues.

The investigator must review the laboratory report, document this review, and record any clinically significant changes occurring during the study in the AE section of the CRF. Clinically significant abnormal laboratory test findings are those that are not associated with the underlying disease, unless judged by the investigator to be more severe than expected for the participant's condition.

All laboratory tests with values considered clinically significant and abnormal during participation in the study or within 48 hours after the last dose of study intervention should be repeated until the values return to normal or baseline or are no longer considered clinically significant by the investigator or study medical monitor.

If such values do not return to normal/baseline within a period of time judged reasonable by the investigator, the etiology should be identified and the sponsor notified.

See [Appendix 6](#) for suggested actions and follow-up assessments in the event of potential DILI.

See [Appendix 7](#) for instructions for laboratory testing to monitor kidney function and reporting laboratory test abnormalities.

Urine drug and cotinine (mandatory) and alcohol breath test (at discretion of investigator) will be performed at screening from Days -28 to -2 and again on Day -1. These tests may be performed at any other time at the discretion of the investigator.

8.3.6. COVID-19 Specific Assessments

Participants will be checked for exposure to positive participant, residence or travel in area of high incidence and COVID-19 related signs and symptoms. Participants will be tested for COVID-19 infection by PCR prior to being admitted to the clinic for confinement and a subsequent COVID-19 test will be performed after 4 days (ie, upon completion of 4 × 24 hours in house), or if they develop COVID-19-like symptoms. Additional testing may be required by local regulations and guidance or by the PI.

8.4. Adverse Events, Serious Adverse Events, and Other Safety Reporting

The definitions of an AE and an SAE can be found in [Appendix 3](#).

AEs may arise from symptoms or other complaints reported to the investigator by the participant (or, when appropriate, by a caregiver, surrogate, or the participant's legally authorized representative), or they may arise from clinical findings of the investigator or other healthcare providers (clinical signs, test results, etc).

The investigator and any qualified designees are responsible for detecting, documenting, and recording events that meet the definition of an AE or SAE and remain responsible to pursue and obtain adequate information both to determine the outcome and to assess whether the event meets the criteria for classification as an SAE or caused the participant to discontinue the study (see Section [7.1](#)).

During the active collection period as described in Section 8.4.1, each participant will be questioned about the occurrence of AEs in a nonleading manner.

In addition, the investigator may be requested by Pfizer Safety to obtain specific follow-up information in an expedited fashion.

8.4.1. Time Period and Frequency for Collecting AE and SAE Information

The time period for actively eliciting and collecting AEs and SAEs (“active collection period”) for each participant begins from the time the participant provides informed consent, which is obtained before undergoing any study-related procedure and/or receiving study intervention), through and including a minimum of 28 calendar days, except as indicated below, after the last administration of the study intervention.

Follow-up by the investigator continues throughout the active collection period and until the AE or SAE or its sequelae resolve or stabilize at a level acceptable to the investigator.

When a clinically important AE remains ongoing at the end of the active collection period, follow-up by the investigator continues until the AE or SAE or its sequelae resolve or stabilize at a level acceptable to the investigator and Pfizer concurs with that assessment.

For participants who are screen failures, the active collection period ends when screen failure status is determined.

If the participant withdraws from the study and also withdraws consent for the collection of future information, the active collection period ends when consent is withdrawn.

If a participant permanently discontinues or temporarily discontinues study because of an AE or SAE, the AE or SAE must be recorded on the CRF and the SAE reported using the CT SAE Report Form.

Investigators are not obligated to actively seek information on AEs or SAEs after the participant has concluded study participation. However, if the investigator learns of any SAE, including a death, at any time after a participant has completed the study, and they consider the event to be reasonably related to the study intervention, the investigator must promptly report the SAE to Pfizer using the CT SAE Report Form.

8.4.1.1. Reporting SAEs to Pfizer Safety

All SAEs occurring in a participant during the active collection period as described in Section 8.4.1 are reported to Pfizer Safety on the CT SAE Report Form immediately upon awareness and under no circumstance should this exceed 24 hours, as indicated in [Appendix 3](#). The investigator will submit any updated SAE data to the sponsor within 24 hours of its being available.

8.4.1.2. Recording Nonserious AEs and SAEs on the CRF

All nonserious AEs and SAEs occurring in a participant during the active collection period, which begins after obtaining informed consent as described in Section 8.4.1, will be recorded on the AE section of the CRF.

The investigator is to record on the CRF all directly observed and all spontaneously reported AEs and SAEs reported by the participant.

As part of ongoing safety reviews conducted by the sponsor, any nonserious AE that is determined by the sponsor to be serious will be reported by the sponsor as an SAE. To assist in the determination of case seriousness, further information may be requested from the investigator to provide clarity and understanding of the event in the context of the clinical study.

Reporting of AEs and SAEs for participants who fail screening are subject to the CRF requirements as described in Section 5.4.

8.4.2. Method of Detecting AEs and SAEs

The method of recording, evaluating, and assessing causality of AEs and SAEs and the procedures for completing and transmitting SAE reports are provided in [Appendix 3](#).

Care will be taken not to introduce bias when detecting AEs and/or SAEs. Open-ended and nonleading verbal questioning of the participant is the preferred method to inquire about AE occurrences.

8.4.3. Follow-Up of AEs and SAEs

After the initial AE or SAE report, the investigator is required to proactively follow each participant at subsequent visits/contacts. For each event, the investigator must pursue and obtain adequate information until resolution, stabilization, the event is otherwise explained, or the participant is lost to follow-up (as defined in Section 7.3).

In general, follow-up information will include a description of the event in sufficient detail to allow for a complete medical assessment of the case and independent determination of possible causality. Any information relevant to the event, such as concomitant medications and illnesses, must be provided. In the case of a participant death, a summary of available autopsy findings must be submitted as soon as possible to Pfizer Safety.

Further information on follow-up procedures is provided in [Appendix 3](#).

8.4.4. Regulatory Reporting Requirements for SAEs

Prompt notification by the investigator to the sponsor of an SAE is essential so that legal obligations and ethical responsibilities toward the safety of participants and the safety of a study intervention under clinical investigation are met.

The sponsor has a legal responsibility to notify both the local regulatory authority and other regulatory agencies about the safety of a study intervention under clinical investigation. The sponsor will comply with country-specific regulatory requirements relating to safety reporting to the regulatory authority, IRBs/ECs, and investigators.

Investigator safety reports must be prepared for SUSARs according to local regulatory requirements and sponsor policy and forwarded to investigators as necessary.

An investigator who receives SUSARs or other specific safety information (eg, summary or listing of SAEs) from the sponsor will review and then file it along with the SRSD(s) for the study and will notify the IRB/EC, if appropriate according to local requirements.

8.4.5. Environmental Exposure, Exposure During Pregnancy or Breastfeeding, and Occupational Exposure

Environmental exposure, occurs when a person not enrolled in the study as a participant receives unplanned direct contact with or exposure to the study intervention. Such exposure may or may not lead to the occurrence of an AE or SAE. Persons at risk for environmental exposure include healthcare providers, family members, and others who may be exposed. An environmental exposure may include EDP, EDB, and occupational exposure.

Any such exposures to the study intervention under study are reportable to Pfizer Safety within 24 hours of investigator awareness.

8.4.5.1. Exposure During Pregnancy

An EDP occurs if:

- A male participant who is receiving or has discontinued study intervention inseminates a female partner.
- A female nonparticipant is found to be pregnant while being exposed or having been exposed to study intervention because of environmental exposure. Below are examples of environmental EDP:
 - A female family member or healthcare provider reports that she is pregnant after having been exposed to the study intervention by ingestion, inhalation, or skin contact.
 - A male family member or healthcare provider who has been exposed to the study intervention by ingestion, inhalation or skin contact then inseminates his female partner prior to or around the time of conception.

The investigator must report EDP to Pfizer Safety within 24 hours of the investigator's awareness, irrespective of whether an SAE has occurred. The initial information submitted should include the anticipated date of delivery (see below for information related to termination of pregnancy).

- If EDP occurs in a participant's partner, the investigator must report this information to Pfizer Safety on the CT SAE Report Form and an EDP Supplemental Form, regardless of whether an SAE has occurred. Details of the pregnancy will be collected after the start of study intervention and until 50 hours after the last dose.
- If EDP occurs in the setting of environmental exposure, the investigator must report information to Pfizer Safety using the CT SAE Report Form and EDP Supplemental Form. Since the exposure information does not pertain to the participant enrolled in the study, the information is not recorded on a CRF; however, a copy of the completed CT SAE Report Form is maintained in the investigator site file.

Follow-up is conducted to obtain general information on the pregnancy and its outcome for all EDP reports with an unknown outcome. The investigator will follow the pregnancy until completion (or until pregnancy termination) and notify Pfizer Safety of the outcome as a follow-up to the initial EDP Supplemental Form. In the case of a live birth, the structural integrity of the neonate can be assessed at the time of birth. In the event of a termination, the reason(s) for termination should be specified and, if clinically possible, the structural integrity of the terminated fetus should be assessed by gross visual inspection (unless preprocedure test findings are conclusive for a congenital anomaly and the findings are reported).

Abnormal pregnancy outcomes are considered SAEs. If the outcome of the pregnancy meets the criteria for an SAE (ie, ectopic pregnancy, spontaneous abortion, intrauterine fetal

demise, neonatal death, or congenital anomaly in a live-born baby, a terminated fetus, an intrauterine fetal demise, or a neonatal death), the investigator should follow the procedures for reporting SAEs. Additional information about pregnancy outcomes that are reported to Pfizer Safety as SAEs follows:

- Spontaneous abortion including miscarriage and missed abortion should be reported as an SAE;
- Neonatal deaths that occur within 1 month of birth should be reported, without regard to causality, as SAEs. In addition, infant deaths after 1 month should be reported as SAEs when the investigator assesses the infant death as related or possibly related to exposure to the study intervention.

Additional information regarding the EDP may be requested by the sponsor. Further follow-up of birth outcomes will be handled on a case-by-case basis (eg, follow-up on preterm infants to identify developmental delays). In the case of paternal exposure, the investigator will provide the participant with the Pregnant Partner Release of Information Form to deliver to his partner. The investigator must document in the source documents that the participant was given the Pregnant Partner Release of Information Form to provide to his partner.

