4.2. Scientific Rationale for Study Design

The objective of the study is to evaluate the effect of a low-fat or high-fat meal on the relative bioavailability of PF-07284890 following single 200-mg dose oral administration using a 100 mg tablet formulation of PF-07284890 in healthy adult participants. A crossover design is used to control variability between participants and account for any period effects. Between each administered single dose, a 5-day washout is proposed to minimize any residual PF-07284890 concentrations prior to start of the next period, which is sufficient based on the observed half-life of approximately 5.7 to 10 hours ([Table 4](#)).

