5.3.5. Photosensitivity

Given the potential for phototoxicity from nonclinical toxicology studies with PF-07284890, participants will be advised to report any reaction to sun exposed skin. In addition, special precautions will be taken to limit any potential photo irritation effect, by minimizing the participants' exposure to light including sunlight, and high intensity UVB light sources such as tanning beds, tanning booths and sunlamps. Participants should be encouraged to apply sunscreen/sunblock daily and to wear clothing that covers areas of exposed skin when outdoors during daylight hours until discharge from the CRU, which is more than 5 half-lives from the last dose of PF-07284890.

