6.8. Treatment of Overdose

For this study, any dose of PF-07284890 greater than the prescribed regimen within a 24-hour time period ± 6 hours will be considered an overdose.

Sponsor does not recommend specific treatment for an overdose.

In the event of an overdose, the investigator/treating physician should:

1. Contact the study medical monitor within 24 hours.
2. Closely monitor the participant for any AEs/SAEs and laboratory abnormalities as medically appropriate for at least 5 half-lives or 28 calendar days (whichever is longer) after the overdose of PF-07284890.
3. Document the quantity of the excess dose as well as the duration of the overdose in the CRF.
4. Overdose is reportable to Pfizer Safety **only when associated with an SAE**.
5. Obtain a blood sample for PK analysis within 7 days from the date of the last dose of study intervention if requested by the study medical monitor (determined on a case-by-case basis).

Decisions regarding dose interruptions or modifications will be made by the investigator in consultation with the study medical monitor as needed based on the clinical evaluation of the participant.

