10.4. Appendix 4: Contraceptive and Barrier Guidance

10.4.1. Male Participant Reproductive Inclusion Criteria

Male participants are eligible to participate if they agree to the following requirements during the intervention period and for at least 28 days after the last dose of study intervention, which corresponds to the time needed to eliminate reproductive safety risk of the study intervention(s):

- Refrain from donating sperm.

PLUS either:

- Be abstinent from heterosexual intercourse as their preferred and usual lifestyle (abstinent on a long-term and persistent basis) and agree to remain abstinent.

OR

- Must agree to use contraception/barrier as detailed below:
 - Agree to use a male condom, and should also be advised of the benefit for a female partner to use a highly effective method of contraception, as a condom may break or leak, when having sexual intercourse with a WOCBP who is not currently pregnant.

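### Section 8.4.5.1 stops collecting partner-pregnancy details 50 hours after the last dose, in conflict with the reproductive-risk period of at least 28 days in Section 10.4.1 and with its own follow-up rule

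*Protocol*

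**What the plan says.** Four statements in the current protocol bear on this point.

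- **Collection window (Section 8.4.5.1).** For EDP in a participant's partner: "Details of the pregnancy will be collected after the start of study intervention and until 50 hours after the last dose".
- **Definition of EDP (Section 8.4.5.1).** "A male participant who is receiving or has discontinued study intervention inseminates a female partner". The definition has no end date.
- **Follow-up (Section 8.4.5.1).** "Follow-up is conducted to obtain general information on the pregnancy and its outcome for all EDP reports with an unknown outcome", and "The investigator will follow the pregnancy until completion (or until pregnancy termination) and notify Pfizer Safety of the outcome".
- **Reproductive-risk period (Section 10.4.1).** Men must not donate sperm, and must be abstinent or use a condom. This applies while they are being dosed, then continues as follows: "for at least 28 days after the last dose of study intervention, which corresponds to the time needed to eliminate reproductive safety risk".

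On timing, the Schedule of Activities (Section 1.3) places the Day 4 assessments at 72 hours after the dose and discharge on Day 4 of Period 3. Section 4.1 has participants confined from Day -1 of Period 1. The safety follow-up contact is 28 to 35 days after the final dose. The SAP does not address pregnancy exposure.

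**The concern.** The protocol gives two post-dose periods for closely related purposes and does not explain the difference. If reproductive risk takes at least 28 days to clear, a rule for collecting partner-pregnancy details should not end on the third day.

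The topic matters for this drug. Section 4.2.2 reports a nonclinical signal of severe developmental toxicity at clinically relevant exposures. Women who enrol must be of non-childbearing potential, so among participants the expected route to an exposed pregnancy is through a male participant's partner. A site that follows the 50-hour sentence literally could treat the details of a pregnancy conceived on, say, Day 10 after the last dose as outside collection, although Section 10.4.1 places it inside the risk period. What is at stake is clear and consistent safety instructions to sites. No estimate from the trial is affected.

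**Working it through.** The protocol gives no derivation for 50 hours, so there is no figure to reproduce. The check is a comparison of texts with unit conversions.

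**Inputs**
- Collection limit: 50 h after the last dose (Section 8.4.5.1).
- Risk period: at least 28 days after the last dose (Section 10.4.1).
- Scheduled discharge: Day 4 of Period 3, about 72 h after the last dose (Section 1.3).

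**Step 1: the two periods in the same units**
- 50 / 24 = 2.08 days.
- 28 × 24 = 672 h.
- 50 / 672 = 7.4%.
- Difference: 672 − 50 = 622 h, and 622 / 24 = 25.9 days.

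**Step 2: position relative to discharge**
- 72 − 50 = 22 h, so the window closes about 22 hours before scheduled discharge.
- It opens at the start of study intervention, which is also during confinement, so the whole window lies inside the stay.
- Risk period remaining after discharge: 672 − 72 = 600 h, and 600 / 24 = 25 days. The window covers none of it.

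**Step 3: the sentence under each possible reading**

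| Reading of the 50-hour sentence | Conflicts with |
|---|---|
| Deadline for recording details | The rule in the same section that a pregnancy is followed until it is completed or terminated, which cannot happen within 50 hours |
| Limit on which exposures count | The at-least-28-day risk period in Section 10.4.1, and the untimed EDP definition in Section 8.4.5.1 |

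The text does not say which reading is meant. Both produce a conflict, so the finding does not depend on choosing one.

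**The case against.** The strongest reply is that the substance is covered elsewhere, and most of this stands.

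- Section 8.4.5.1 requires every EDP to be reported within 24 hours of awareness, with no end date. It also treats abnormal pregnancy outcomes as serious adverse events, lets the sponsor ask for more information, and provides a release form for the pregnant partner.
- Section 10.3.3 repeats that all instances of EDP are reported.
- Section 5.3.1 tells participants to call at once if a partner's pregnancy is known or suspected.
- Section 8.4.1 keeps adverse-event collection open for at least 28 days, and there is a contact at 28 to 35 days.

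A reader might therefore infer from the 25.9-day difference that partner pregnancies would go unreported in that interval. The documents do not support that inference, because the reporting and follow-up duties carry no 50-hour limit.

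A second reply is that the two periods do different jobs: 28 days governs participant behaviour, and 50 hours governs data collection. This is fair as far as it goes. However, Section 10.4.1 ties its period to the time needed to eliminate reproductive safety risk, and it is hard to see why collection of the related pregnancy details should stop earlier.

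Two further inferences are tempting and are not relied on here.

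- A reader might take 50 hours as five times the upper end of the "observed half-life of approximately 5.7 to 10 hours" in Section 4.2, and so as a deliberate exposure window. The arithmetic fits (5 × 10 = 50), but the protocol never states this origin or that reading.
- A reader might cite the overdose rule in Section 6.8, "for at least 5 half-lives or 28 calendar days (whichever is longer) after the overdose of PF-07284890", as showing that 28 days must govern. That rule concerns monitoring after an overdose and says nothing about partner pregnancy. Section 5.3.5, on photosensitivity, even treats more than five half-lives as enough for its own purpose.

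**Conclusion.** The 50-hour limit is wrong as written. It conflicts with Section 10.4.1 and with the definition and follow-up rule in its own section, and no other text reconciles them. The window is about 2.1 days against at least 28 days, and it closes before scheduled discharge.

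The severity is minor: this is an internal inconsistency in one safety-collection rule. The 24-hour reporting duty and follow-up to outcome remain in force, and no lost data item is shown. The PK endpoints, models, analysis sets and sample size are unaffected.

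The statement about discharge assumes a participant who completes all three periods and leaves on schedule. Someone who stops early could leave within 50 hours of the last dose. The mismatch between sections does not depend on that assumption.

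**What to change.** In Section 8.4.5.1, replace the 50-hour limit with: *until at least 28 days after the last dose; every reported EDP is followed to pregnancy outcome regardless of when it is reported*. Alternatively, delete the time limit and let the existing reporting and follow-up rules stand alone. Either way, the wording should not put an end date on the EDP definition, which now has none.

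The cost is one phrase in the protocol. No visit, sample or procedure is added, because a contact at 28 to 35 days is already scheduled. The SAP needs no change.
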